Twitter-enabled Mobile Messaging for Smoking Relapse Prevention (Tweet2Quit)

NCT02823028

Study Protocol and Statistical Analysis Plan

University of California Irvine IRB approval of this final modification: 6/28/2019

Uploaded by [name] [name], University of California, Irvine

Upload this completed narrative and any supplemental documentation to the [IRB Application](#).

**IRB USE ONLY –
HS#:**

Lead Researcher Name: [name]

Study Title: Twitter-enabled Mobile Messaging for Smoking Relapse Prevention, Phase 2

ABSTRACT

Provide a non-technical summary of the proposed research that can be understood by IRB members with varied research backgrounds, including non-scientists and community members. The summary should include a brief statement of the **purpose of the research** and a brief description of the **procedure(s)**. *This summary should not exceed more than 250 words.*

Many smoking cessation treatments exist but engagement remains low and relapse rates remain high, suggesting the need for more innovative, accessible and interactive treatment strategies. In 2011-2014, we developed, piloted and evaluated a novel, interactive, live treatment for providing peer-based social support to smokers who are trying to quit, via Twitter on mobile phones. We refer to this as Phase I (HS# 2010-7990) of our research, because we developed a treatment protocol for this novel treatment and conducted a randomized controlled trial comparing this treatment to a base website intervention. HS# 2010-7990 was concluded in 2014. In the current Phase II we propose to continue testing Tweet2Quit by comparing randomized control and treatment groups with both coed and women-only treatment groups and biochemical verification of abstinence.

SECTION 1: BACKGROUND AND SIGNIFICANCE OF THE RESEARCH

1. Provide the scientific or scholarly **rationale** for the research. Describe the relevant background information and the specific gaps in current knowledge that this study intends to address.

Traditional quit smoking and drug use programs remain underutilized due to cost and inconvenience and relapse is common. To increase utilization in such programs, researchers and practitioners are urgently seeking to harness the power of social media. Wildly popular social media sites such as Facebook and Twitter allow users to stay connected to individuals and groups in real time and to share content at virtually no cost¹. Social media is entrenched in US households with 73% of online adults using social media sites, 42% using multiple sites, and the majority visiting them daily². Twitter is the dominant open social media site with a reported 200 million active users posting 400 million tweets daily and with 44% growth from 2012-2013³. There are already over 140 reported medical and health care uses of Twitter⁴. Relative to Facebook, Twitter has superior programming language (APL), and has continued to rise in use substantially (whereas Facebook use has not); and it is easier to keep group member communications private (i.e., within the group only).

Because of its broad reach and appeal, real-time interactivity and free cost, social media looks highly promising for delivering tobacco and other addiction treatment interventions. Also, because social media often elicits spontaneous, honest disclosures that are automatically catalogued, it can yield insight into oft-concealed

phenomena such as co-use of addictive drugs and how this might trigger relapse, suggesting possible new interventions. Despite social media's apparent promise, and observational evidence indicating that existing socially mediated forums may increase patient compliance⁵, social media's potential for delivering interventions and developing new treatment approaches has not yet been fully realized.

Our intervention will address issues of engagement by testing and improving a socially-mediated intervention that already has been shown to produce good engagement. We believe that engagement happens due to the development of a sense of online community through interpersonal interactions online^{7,8}. In response to calls for the application of systems science to public health⁹, we intend to study online engagement by applying network analysis¹⁰.

2. Describe the **purpose, specific aims or objectives**. Specify the hypotheses or research questions to be studied.

Aim 1

Our first primary aim is to test the 6-month efficacy of Tweet2Quit with biochemical verification of abstinence. We hypothesize that relative to usual care (n=240), Tweet2Quit-coed groups (n=480) will achieve significantly greater bioconfirmed sustained abstinence out to 6-months follow-up.

Aim 2

Our second primary aim is to test whether women do better in Tweet2Quit women-only versus coed groups. We hypothesize that women in Tweet2Quit will achieve significantly greater bioconfirmed 6-month abstinence in woman-only groups (n=240) vs. coed groups (n=240 women in those groups).

Secondary Aims will test the same hypotheses, however, based on 3-month (end of treatment) sustained and bioconfirmed abstinence rates and we will also test 7-day point prevalence abstinence at 1, 3, and 6 months.

Exploratory Aims will study the Tweet2Quit groups' social network structures with a focus on the identification of buddy pairs and social brokers, both via baseline theoretically-based measures and observed tweeting behaviors. In particular, we will test the following conceptual models positing how dyadic tie strength and betweenness centrality may serve as mechanisms of effects and promote smoking abstinence.

- *Better matched buddy pairs based on demographics → dyadic tie strength → dyad abstinence.*
- *Better social brokers based on self-monitoring → betweenness centrality → group tweets → group abstinence.*
- *These links will be stronger for women in women-only groups vs. women in coed groups of Tweet2Quit.*

3. List up to **ten relevant references/articles** to support the rationale for the research.

1. Joinson A, N. "Looking at", "looking up" or "keeping up with" people? Motives and use of facebook. Proceedings of the SIGCHI Conference on Human Factors in Computing Systems; April 5-10, 2008, 2008; Florence, Italy.
4. Baumann P. *140 Health care uses for twitter.* 2009; <https://vpn.nacs.uci.edu/+CSCO+0h756767633A2F2F637576796F6E687A6E61612E70627A++/140-health-care-uses-for-twitter/>. Accessed January 16, 2009.

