In Years 2-5, we will achieve Aim 1 and 2: to conduct a 3-arm cluster-randomized controlled trial of the 2nd generation *Tweet2Quit* Twitter-delivered group intervention. Both treatment (coed and women only) and control participants will receive a web-based quit plan referral, 8-weeks of nicotine patches and 8-weeks of nicotine gum/lozenges but the control groups will get this without Twitter support. Cohorts of 20-30 smokers that have passed the screening will be randomly assigned to treatment coed (with control) or treatment women only and then treatment participants will be grouped into demographically homophilous dyads or buddy pairs. Thus, both dyads and cohorts will be nested factors in the analyses.

Although UCI is collaborating with UCSF, Investigator [name] is not engaged in human-subjects research, given he is not interacting with participants, and he is not accessing identifiable data. UC Reliance #977 is *inactive*

Recruiting is a continuous ongoing activity and a new group is created once 20-30 applicants have completed the enrollment process. [name] will create a randomization table that will determine, e.g., every month, if the next cohort to be recruited will be coed or women-only, with 2/3rds of the cohorts being

coed and 1/3rd being women-only. A coed cohort of 30 smokers will have a minimum of 6 men (max. 10) and a maximum of 24 women (min. 20). Then, [name] will randomize 20 of these smokers to coed treatment and 10 smokers to coed control with the provisos that there be (a) a minimum of 4 men in coed tweet2quit (to ensure a critical mass), and (b) even numbers of men and even numbers of women in coed tweet2quit, i.e., 4, 6 or 8 not 3, 5 or 7 (for buddy pairing within gender). [name] will not see any identifiable subject data; he will only see anonymized subject numbers such as G01P01. If the treatment cohort to be recruited is women-only, then only women will be recruited. Any men that we also recruit will be waitlisted and placed in the next coed cohort. As treatment to control ratios of genders may not be equivalent, gender will be taken into account as a covariate during analysis.

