After recruits have passed the initial screen, first they will pass a verification check for their phone, email and webcam, or they will not be eligible to participate. Next, each recruit will complete a second screening survey to confirm eligibility in case of long lapse of time. In addition we will contact them via webcam to verify their identities and confirm their interest in participation. This will be a trial run for the remote collection of salivary cotinine test pictures for bioconfirmation of abstinence that will occur at 3 and 6 months that will take place via webcam with photo IDs.

The screening survey will assess demographic variables that will be used for dyad formation. After the randomization to study condition, the 20 smokers in each treatment group will be coupled into 10 demographically homophilous dyads or buddy pairs based on certain screening data. To determine the specific variables to use to form homophilous dyads, we will rely on analyses that are underway that correlate similar demographics with tie strength in our prior Tweet2Quit groups.

Standard Resources given to Participants (Initial and Main Study Groups)

All participants, regardless of assignment, will receive an integrated smoking cessation plan to ensure an equitable and adequate intervention dose for all participants. The integrated plan, including free nicotine patches and gum/lozenges, referral to the NCI Smokefree.gov Quit Guide and encouragement to set a quit date, represents a standard intervention for people desiring to quit smoking. The purpose of our study is to examine the potential efficacy of including Twitter-enabled interactive peer texting as a low-cost, accessible added intervention to the standard protocol. Participants assigned to control will not be prevented from following the very large existing Twitter quit smoking groups that are publically available on Twitter; but they will not be assigned to small, private quit-smoking groups with computer-generated feedback, like the treatment groups will be. Our proposed intervention is consistent with U.S. Clinical Practice Guidelines, which recommends nicotine-replacement therapy and the setting of a quit date, consistent with our protocol.

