## Tweet2Quit Statistical Analysis Plan

## Statistical Analyses

Dropout rates are examined by condition. Every effort is made to limit the amount of missing data from survey attrition by doing persistent follow-up with participants and contacting their preidentified collaterals (family members and friends) to urge survey completion. Before analysis, we will examine baseline predictors of attrition. If it appears that attrition is related to measured aspects of the participants, we will include those measures as covariates in the models. Sensitivity analyses will check that the methods of dealing with missing data do not have a major impact on the results. We will repeat the attrition analyses under 2 different models, one in which the missing data are assumed to be positive for smoking and one using only the respondents who did not have missing data. We expect to find that although estimates may change some, the conclusions generated by the modeling should not change.

For primary hypothesis testing of sustained abstinence at 6 months, we will use the 6-month post quit date survey (based on the quit date selected by the participant at the beginning of the study) and biochemical salivary cotinine verification. To test the *primary aim 1 hypothesis*, analyses will compare sustained abstinence for participants randomized to coed Tweet2Quit treatment versus control. Sustained abstinence will be modeled as a function of study arm (coed Tweet2Quit or control), gender, cohort, and individual using a logistic model and generalized estimating equations (Proc Genmod in SAS) to account for the clustering of individuals within cohort. Our statistical methods will use all the data in parameter estimation. We will test the coefficient of the study arm or treatment condition parameter, doing so by gender if there is a treatment condition by gender interaction.

The same type of generalized logistic model, but focusing on women, will be used to test the *primary aim 2 hypothesis*, on whether women will achieve greater 6-month sustained, bioconfirmed abstinence if randomized to a women-only versus coed Tweet2Quit treatment group. Secondary hypotheses concerning sustained abstinence at 3 months (ie, at treatment end) and point prevalence (prior 7 day) abstinence at 1, 3, and 6 months will be tested using the same modeling approaches.

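### Aim 2 states 240 women in the coed treatment groups, but the coed composition rule yields 288 to 384

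*Protocol*

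**What the plan says.** Protocol Section 1, item 2, gives the arm sizes. For Aim 1 they are "relative to usual care (n=240), Tweet2Quit-coed groups (n=480". For Aim 2, women are compared "in woman-only groups (n=240) vs. coed groups (n=240 women in those groups".

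Protocol Section 6A, Main Phase Randomized Controlled Trial, gives the rule that builds the coed arm:

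- Recruitment: "A coed cohort of 30 smokers will have a minimum of 6 men (max. 10) and a maximum of 24 women (min. 20".
- Allocation: the statistician "will randomize 20 of these smokers to coed treatment and 10 smokers to coed control".
- Conditions on the treatment group: "a minimum of 4 men in coed tweet2quit (to ensure a critical mass", and "even numbers of men and even numbers of women in coed tweet2quit, i.e., 4, 6 or 8 not 3, 5 or 7".

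The Enrollment Process text in the same section fixes the group size: "the 20 smokers in each treatment group will be coupled into 10 demographically homophilous dyads or buddy pairs".

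The SAP (Statistical Analyses) fits the Aim 2 model to women. For Aim 1 it tests the treatment coefficient, "doing so by gender if there is a treatment condition by gender interaction".

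**The concern.** With 480 people in the coed arm, 240 women means 240 men, or 10 of each per group of 20. The composition rule makes men a minority in every coed cohort and lists at most 8 men per treatment group. The two statements describe different trials.

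Three things depend on which is meant:

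- **Sample size.** The 240 is the planned size of one side of a primary comparison, and any precision or power statement for Aim 2 would use it.
- **The comparator.** Aim 2 asks whether women do better without men in the group, so the sex mix of the coed groups is part of the question. A group that is two-thirds to four-fifths women is a different contrast from one that is half women.
- **Men in Aim 1.** If the SAP's by-gender test is triggered, the men's estimate would rest on far fewer treated men than Aim 2 implies.

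**Working it through.** **Inputs.** Section 1: coed arm 480, control 240, women-only 240, stated coed women 240. Section 6A: 30 per coed cohort with 6 to 10 men; 20 to treatment and 10 to control; 4, 6 or 8 men per coed treatment group; 20 per treatment group.

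**Step 1: number of coed groups.** 480/20 = 24. Controls give the same answer: 240/10 = 24. Women-only groups: 240/20 = 12. The ratio 24:12 matches the two-thirds to one-third cohort split in Section 6A. The total, 480 + 240 + 240 = 960, plus the pilot cohort of 20, equals the 980 in the Section 3 enrollment table. The group count is therefore secure, and every other stated number fits.

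**Step 2: try to reproduce the stated 240.** 240/24 = 10 women per group, so 10 men per group. That is outside the listed 4, 6 or 8.

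**Step 3: limits under the rule.** Women = 24 × (20 − men per group).

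| Men per treatment group | Women in arm | Men in arm | Share women |
|---|---|---|---|
| 4 | 24 × 16 = 384 | 96 | 80% |
| 6 | 24 × 14 = 336 | 144 | 70% |
| 8 | 24 × 12 = 288 | 192 | 60% |

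Intermediate totals arise when groups differ. The stated 240 is 48 below the lower limit.

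**Step 4: expected totals.** The protocol does not say how the draw is made to satisfy its conditions. Assume a random draw of 20 from 30 (hypergeometric), conditional on 4, 6 or 8 treated men.

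| Men in cohort of 30 | Mean treated men | Expected women, 24 × (20 − mean) |
|---|---|---|
| 6 | 4.30 | 376.8 |
| 7 | 4.80 | 364.8 |
| 8 | 5.38 | 350.8 |
| 9 | 6.01 | 335.7 |
| 10 | 6.63 | 320.9 |

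This is 34% to 57% above 240. Women would be about 67% to 79% of the arm (320.9/480 to 376.8/480). Expected men are 480 − 376.8 = 103 to 480 − 320.9 = 159. Without the evenness and minimum conditions the expected women are 320 to 384, so the conditions matter little.

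**Step 5: looser reading.** Suppose the list 4, 6 or 8 only illustrates even numbers, and 10 treated men is allowed. Then 240 women needs 10 men in all 24 cohorts, every one of them treated. The chance is 0.012 in a single 10-man cohort, and the expected total with 10 men per cohort is 319.9. Men across both coed arms are capped at 24 × 10 = 240, so control would contain no men.

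**Step 6: effect on Aim 2 precision.** With n coed women in 24 groups, 240 women in 12 groups of 20, and a common abstinence rate p:

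SE = sqrt( p(1−p) × [ (1 + 19·ICC)/240 + (1 + (n/24 − 1)·ICC)/n ] )

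The documents give no p or ICC. Both are assumed here, with p = 0.20; the percentage change does not depend on p if it is equal in both arms.

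| ICC | n = 240 | n = 321 | n = 377 | SE reduction |
|---|---|---|---|---|
| 0 | 0.0365 | 0.0341 | 0.0330 | 6.5% to 9.5% |
| 0.02 | 0.0413 | 0.0393 | 0.0383 | 5.0% to 7.2% |
| 0.05 | 0.0476 | 0.0459 | 0.0451 | 3.6% to 5.2% |

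Buddy-pair clustering is left out of this formula.

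**The case against.** The strongest reply is that nothing breaks. The SAP model uses whatever women are enrolled, 240 does not enter it, and more coed women help. The protocol already expects unequal gender ratios between treatment and control and adjusts for gender. The 240 men are inferred by subtraction, and no target is set for men. This all stands, and it is why the point is not a claim that Aim 2 is underpowered. But the remark on gender ratios concerns balance between arms and does not explain the 240.

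A second reply is that 288 and 384 are themselves extremes. With 10 men in every cohort, 8 treated men in all 24 groups has probability about 0.38 to the power 24, or 1 in 10 billion. A total of 384 has about a 2% chance even with 6 men in every cohort. That is fair: they are arithmetic bounds, and the expected range is the better planning figure, provided its random-draw assumption is stated with it.

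Other readings of 240 fail. Women in both arms of the coed cohorts would number 24 × 20 = 480 to 24 × 24 = 576. The looser cohort size of 20 to 30, also in Section 6A, does not help, because composition and allocation are given only for 30 and treatment groups are fixed at 20.

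**Conclusion.** The inconsistency is real. The bounds need only the stated group size and composition rule. The expected range also needs the random-draw assumption, but it barely moves under the alternatives tried. The precision effect is favourable, at roughly 4% to 10% smaller standard errors over the ICCs assumed. The documents do not show which section is out of date. The point should be corrected because it misstates a primary-aim sample size and the sex mix of the coed comparator, not because a test is compromised.

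**What to change.** Reconcile Section 1, Aim 2, with the composition rule in Section 6A.

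- **If the composition rule stands:** restate Aim 2 as 240 women in 12 women-only groups versus an expected 321 to 377 women in 24 coed groups (limits 288 to 384), and give the allocation assumption behind the expected figure. State that the coed arm is 60% to 80% women by rule, and about 67% to 79% in expectation. Base any Aim 2 precision or power statement on those numbers. Note the expected 103 to 159 treated men where the by-gender test is described. This costs wording only: recruitment, randomization and analysis do not change.
- **If 240 coed women was intended:** the composition rule must be changed instead. That affects recruitment and possibly randomization, so it is not a wording change.

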3. GCP – Social and Behavioral Research Best Practices for Clinical Research

SECTION 3: SUBJECT POPULATION(S) (INDIVIDUALS/RECORDS/BIOSPECIMENS)

A. Individuals To Be Enrolled on this UCI protocol (Persons/Records/Biospecimens)

1. Complete the table of participant enrollments below. *Include additional rows for subject category/group, as needed.*
2. If the study involves the use of existing records or biospecimens, specify the maximum number to be reviewed/collected, and the number needed to address the research question.

Category/Group (e.g., adults, parents, children)	Age Range (e.g., 7-12, 13-17, 18 or older)	Maximum Number to be Consented or Reviewed/Collected (include withdrawals and screen failures)	Number Expected to Complete the Study or Needed to Address the Research Question
Adults	21-59	3000	980
Total: 3000			

B. Eligibility Criteria

1. Identify the criteria for inclusion and exclusion.

For both the Initial and Main Phases, we will recruit adult smokers, 21 to 59 years old, who intend to quit in the next 30 days. We will offer 8 weeks of free nicotine patches and 8 weeks of free nicotine gum/lozenges to all participants, which are relevant and meaningful incentives and *recommended for cessation*. We will recruit by putting ads on Google (donated), in order to reach those who might not use quit-smoking call-in lines or websites. We will inform people of our trial using our free Google ads that will appear when people search for relevant keywords or go to content pages that contain those keywords. An ad will be placed on SmokeFree.gov to further support advertising the study. We will also be recruiting with similar ads on Facebook. Additionally on Facebook, we will be advertising to an English and Spanish-speaking bilingual population using language targeting through Facebook's advertising interface. We cannot currently provide our intervention in Spanish but we hope to attract bilingual Spanish-English participants.

We will be creating groups that contain only females. Males will be excluded from these groups, but not the study. Males will be randomly allocated to one of the coed or control condition.

2. If eligibility is based on age, gender, pregnancy/childbearing potential, social/ethnic group, or language spoken (e.g., English Speakers only), provide a **scientific rationale**.

Not applicable: Subject eligibility is not based on these factors.

We are excluding participants below the age of 21 because California has increased the smoking age to 21 and other states are beginning to do so. Therefore, in the future, it might not even be possible to provide the nicotine replacement therapy that is essential to our study to minors under the age of 21. Non-English speakers will be excluded because the intervention requires communication between participants and English is the national language that participants can communicate in. In other words, all participants must be able to speak English so that they can communicate with other group members. Without communication the participants won't be able to receive the intervention. Even though there is no participant communication in the control groups, as groups are randomly assigned, all must be able to speak English. It is possible to make groups for other languages, but with the resources available to us, this is not feasible at the time. We attempted to test the study in other languages and countries, but have not found funding yet. This study is to test the intervention in the USA that can be replicated in other languages and countries should the study prove successful.

3. If American Indian or Alaska Native Tribes will be included in the research:

- a. Specify the name of the Tribe and
- b. Specify whether there is Tribal Law that may be applicable to this research and that provides additional protections for subjects (i.e., additional information to be disclosed in the consent process).

Not applicable: American Indian or Alaska Native Tribes are not included in the research.

<Type here>

C. PRE-SCREENING AND DETERMINING ELIGIBILITY WITHOUT INFORMED CONSENT

1. IMPORTANT NOTES:

- a. This section is **Not applicable** to research that is funded/supported by the Department of Justice (DOJ)
- b. This section addresses pre-screening activities that are performed **without the written informed consent of the prospective subject or legally authorized representative (LAR)**. This may be allowed without requesting a waiver of informed consent **IF the following guidelines are utilized:**

X **Not applicable:** Information and/or biospecimens will not be obtained for the purpose of screening, recruiting, or determining eligibility of prospective subjects. *Skip to Section 4.*

Study team will obtain information through **oral or written communication** with the prospective subject or LAR (i.e. self-report of medical information; medical records will not be screened).

*Submit [recruitment script/s](#) for IRB approval. Be sure to address minimum recruitment requirements and address **the following guidelines**:*

- i. *Privacy: The script must address the case where someone other than the potential subject receives the communication. Please be mindful of privacy considerations (i.e., do not disclose any private information – such as a patient diagnosis). Limit phone contact / messages to no more than 5 attempts.*
- ii. *Expertise: Study team member/s contacting potential subject must be knowledgeable and able to answer questions related to the screening and the main study.*
- iii. *Specific Information: Include a description of the information and/or biospecimens that will be obtained for the purpose of screening, recruiting, or determining eligibility and the reasons for performing the screening tests.*
- iv. *Confidentiality: Include a statement that informs the potential subject that if they are not eligible to participate in the study that the identifiable information and / or biospecimens will not be used for research purposes and will be destroyed at the earliest opportunity consistent with conduct of the research.*

Study team will **screen medical records** to determine subject eligibility.

Complete [Appendix T](#) to request a partial waiver of HIPAA Authorization.

Study team will **screen medical records** to determine subject eligibility **under IRB approved screening protocol**. Specify HS#: <[Type here](#)>

Study team will **screen non-medical records** (i.e., student records) to which they have access to determine subject eligibility. Specify: <[Type here](#)>

For research accessing student records, check here to confirm that evidence of FERPA¹ compliance has been / will be obtained (and on file) from the local school/district site prior to the initiation of research.

Study team will **access stored identifiable biospecimens**.

2. For studies that will **screen medical records**, explain how the study team will access the clinical data. *Access to UCI Medical Center medical records for research purposes outside the capacity of the Honest Broker Services, such as access to physician notes, must be obtained from the Health Information Management Services.*

¹ 34 CFR 99: [Family Educational Rights and Privacy Act](#) (FERPA) applies to this research.

Not applicable: This study does not involve the screening of medical records.

How Obtained: Indicate all that apply:

The study team will request specific patient information/data from UCIMC Health Information Management Services.

The study team will review their UCI patients' records and abstract data directly from those records.

The study team will request specific patient information/data from UCI Health Honest Broker Services. Describe the following:

Cohort selection criteria (e.g., use the available Clinical Terms from the Cohort Discovery Tool such as Demographics: Gender, Diagnoses: Asthma, Procedures: Operations on digestive system): [**<Type here>**](#)

Expected cohort size/patient count: [**<Type here>**](#)

Cohort attributes or data elements (e.g., lab test values, medication, etc.): [**<Type here>**](#)

The study team will review non-UCI Health records and abstract data directly from those records. Describe the following:

Specify the non-UCI Health records that will be screened: [**<Type here>**](#)

Explain how the study team has access to this clinical data: [**<Type here>**](#)

Other; explain: [**<Type here>**](#)

3. For studies that will **screen existing biospecimens**:

- a. Indicate the source of the biospecimens and explain how the existing biospecimens will be obtained.
- b. Indicate whether the biospecimens were originally collected for research purposes.

Not applicable: This study does not screen existing biospecimens.

How Obtained: Indicate all that apply:

UCI Health Pathology Biorepository

Other UCI-Health Entity; specify: [<Type here>](#)

Non-UCI Entity; specify: [<Type here>](#)

Other; explain: [<Type here>](#)

Originally collected for research purposes:

NO – Please explain: [<Type here>](#)

YES – UCI IRB approval granted under IRB protocol number (i.e. HS#): [<Type here>](#)

YES – Non-UCI IRB approval granted. Confirm one of the following:

A copy of the IRB Approval Notice and Consent Form for the original research collection will be submitted with the IRB application (APP). The IRB Approved Consent Form does not preclude the proposed activity.

A copy of the commercial Vendor Policy or a Letter from the Vendor attesting that the information was collected and will be shared in an appropriate and ethical manner will be submitted with the APP. The vendor's policy does not preclude the proposed activity.

SECTION 4: RECRUITMENT METHODS

1. Indicate which recruitment methods will be utilized. Check all that apply:
2. Submit the required supplemental materials.

Advertisements must adhere to UCI [Recruitment Guidelines](#). Various templates are available on the HRP webpage [Application and Forms](#) (see sub-section HRP and then Recruitment Templates).

This study involves no direct contact with participants (i.e., passive observation of public behavior or secondary use of information/biospecimens). ***Skip to SECTION 5.***

Method	Required Supplemental Materials
 Flyers	Submit flyer(s)
 Newspaper Advertisement	Submit ad(s)
 Radio / Television Advertisement	Submit scripts(s)
 Online Advertisements – Including Social Media	Submit text, page mock up or description of posting including any images.
 Letters of Emails	Submit template letter(s) or email(s)
 Phone Call	Submit phone script
 Group or Class Presentation	Submit outline of presentation and any materials to be provided to participants
 Social Sciences Human Subject Lab (SSHSL)	None
 Other (specify): <Type here>	Submit the recruitment materials

3. Describe when, where, by whom and how potential participants will be approached.
4. If posting on your Facebook page or other social media sites, please explain.
5. If you will recruit by e-mail, phone, etc., explain how the researcher will obtain the participants' contact information.

For both the initial and main study groups, we will recruit adult smokers, 21 to 59 years old, who intend to quit in the next 30 days. We will offer 8 weeks of free nicotine patches and 8 weeks of nicotine gum or lozenges to all participants, which are relevant and meaningful incentives and recommended for cessation. We will recruit by putting ads on Google (donated) and Facebook (paid), in order to reach those who might not use quit-smoking call-in lines or websites. We will inform people of our trial using ads that will appear when people search for relevant keywords on Google or post the keywords on Facebook (e.g., quit smoking, free nicotine patches). We receive free Google ads through the study's participation in the Google Grant program that supports the work of nonprofits. On Facebook, the ads will include small suitable images (which are required), e.g., cigarettes, cigarette packs, and people of different ethnicities. See file Advertising Image Options.docx for examples. Both Google AdWords and Facebook will use geographical targeting to recruit a more diverse group of participants (e.g., Detroit to target African Americans and Miami to target Hispanics/Latinos). There are general Facebook and Google ads to target everyone as well as specific ads to target minorities and other races (e.g. African American, etc.) We will be additionally advertising to a bilingual English and Spanish-speaking population on Facebook using language targeting options. Any major changes in recruitment strategies will only be conducted after IRB approval is obtained by filing an EMOD.

SECTION 5: INFORMED CONSENT PROCESS

1. **Submit the Consent, Study Info Sheet, Courtesy Letter, Assent document(s).** *Note: After IRB Approval, distribute to participants the version of the document with the IRB-approval information in the footer.*
2. Identify the specific **steps for obtaining consent**. See [Guidance for Consenting Process](#).

Check all that apply:

Signed informed consent will be obtained. *Customize the Consent for SBE Research.*

Oral / Implied informed consent will be obtained (i.e., requesting a waiver from obtaining signed informed consent). *Customize the [Study Information Sheet](#) and Complete Appendix P.*

Note: If obtaining consent online (e.g., research involves completing a survey electronically administered via AMT, EEE, etc.), participants should:

- *View the Consent/Study Info Sheet prior to participation*
- *Be prompted to verify they meet the eligibility criteria, and*
- *Indicate their willingness to participate in the research (e.g., click "Yes").*

Requesting to seek surrogate consent from the subjects' LAR. Surrogate consent may be considered only in research studies relating to the cognitive impairment, lack of capacity or serious or life-threatening disease and conditions of the research subjects. *Complete Appendix E.*

Informed consent will NOT be obtained (i.e., requesting a complete waiver of informed consent). *No contact with participants; using existing data, records, charts, biospecimens, etc. Complete Appendix O. Skip to Section 6.*

3. If medical records will be accessed for research purposes, identify the specific steps for obtaining HIPAA authorization.

For additional information, see [Protected Health Information \(HIPAA\)](#). Templates are available on the HRP webpage [Application and Forms](#) (see sub-section HRP, HIPAA Documents).

Not applicable: Medical records will not be accessed for research purposes.

Total waiver of HIPAA Authorization – No HIPAA authorization will be obtained (i.e., no direct contact with participants). *Submit Appendix T.*

Written (signed) HIPAA Authorization will be obtained – A signature is required.
Customize the HIPAA Research Authorization Form template.

4. Indicate where the consent process will take place.

- In a private room
- In a waiting room
- In an open unit
- In a group setting
- The internet
- In public setting
- Over the phone
- Other (specify): [<Type here>](#)

5. Specify how the research team will assure that subjects or their LAR have sufficient time to consider whether to participate in the research.

Subjects or their LAR will be allowed to take home the unsigned consent form for review prior to signing it.

Subjects or their LAR will be allowed [<Type here>](#) hours to consider whether to consent.

Other (specify): [The subjects or their LAR will be able to download a digital copy of the Information Sheet to read over before considering whether to participate in the research.](#)

6. If children (anyone less than 18 years old) are participants, please describe the parent/legal guardian permission process and the child assent process.

Not applicable: Children are not included in the research.

No parental permission or child assent will take place.

Parental Permission Process: [<Type here>](#)

Child Assent Process: [<Type here>](#)

7. If study team members will approach their own students or employees:

- a. Explain what precautions will be taken to minimize potential undue influence or coercion.
- b. Explain how compromised objectivity will be avoided.

[See HRPP Policy for more information on this topic.](#)

Not applicable: Study team will not approach their own students or employees.

Specify how undue influence or coercion will be minimized: [<Type here>](#)

Specify how compromised objectivity will be avoided: [<Type here>](#)

8. Will this study include Non-English Speaking Participants?

9. Specify in 'Section 2: Study Team' who will be responsible for interacting with non-English speaking participants.

Not applicable: No consent process will take place.

Only individuals who can read and speak English are eligible for this study.

The English version of the consent materials will be translated for non-English speaking participants once IRB approval is granted. An interpreter will be involved in the consenting process. **Note:** *After IRB Approval, distribute to participants the version of the document with the IRB-approval information in the footer.*

10. If deception or incomplete disclosure is involved:

Not applicable: No deception or incomplete disclosure is involved.

Confirm that the following documents will be submitted with the APP:

Debriefing Script

Appendices O (Alteration of Consent) and G (Deception)

11. Release Form: If publications and/or presentations will include **identifiable information**, specify how the study team will obtain permission from participants. Please submit a 'Release Form'

N/A

SECTION 6: RESEARCH METHODOLOGY/STUDY PROCEDURES

A. Study Design and Procedures

1. Provide a **description of the proposed research** (e.g., pilot testing, intervention/interaction/data collection, and follow-up) and **procedures** (e.g., surveys, interview, focus group, and observation). See Guidance for Online Research.
 - a. Specify **where** the research will take place (e.g., UCI, local public schools, international site, private business, etc.).
 - b. Include an explanation of the study design (e.g., randomization, cross-sectional, longitudinal, etc.).
 - c. Indicate how much **time will be required of the participant**, per visit and in total for the study.
 - d. If a procedure will be completed more than once (e.g., multiple visits, pre and post survey), indicate **how many times** and the **time span** between administrations.
